8.3.4 Independent Rater Assessments

Participants will have two CAPS-5 assessments during the treatment period of the study (Visits 8 and 13). An IR from the IR Pool will conduct the assessments via telemedicine. These assessments may be recorded to establish inter-rater reliability. The results may be shared with site staff, but the IR Coordinator will enter the data. The IR will also administer the DSP-I and SDS at these time-points:

- CAPS-5 T2 (Visit 8): 3 weeks after Experimental Session 1 (Visit 5), between Integrative Session 1.2 (Visit 7) and Integrative Session 1.3 (Visit 9)
- CAPS-5 T3 (Visit 13): 3 weeks after Experimental Session 2 (Visit 10), between Integrative Session 2.2 (Visit 12) and Integrative Session 2.3 (Visit 14)

8.4 Follow-up Period and Study Termination

8.4.1 Follow-up Period

After the last Integrative Session 3.3 (Visit 18), participants will enter follow-up for approximately 4 weeks (+/- 2 weeks) with no protocol required visits until the final CAPS-5 assessment (Visit 19) followed by a Study Termination (Visit 20). Participants will have access to therapy teams for support if needed, and additional visits via phone, telemedicine, or in person

can be scheduled if requested. Participants will continue to comply with protocol requirements for concomitant medications until after Study Termination.

8.4.2 Final Independent Rater Assessment

Participants will have a final CAPS-5 assessment at the completion of the follow-up period (Visit 19). An IR from the IR Pool will conduct the assessments via telemedicine. These assessments may be recorded to establish inter-rater reliability. The IR Coordinator will enter the data in stand-alone database. The results may be shared with site staff during supervision by the therapy training team. Although there are allowable windows for all visits throughout the protocol, the Primary Outcome CAPS-5 T4 assessment must be completed 18 weeks (+/- 3 weeks) after the Baseline CAPS-5 assessment and within 8 weeks (+/-2 weeks) of Experimental Session 3 (Visit 15). Participants who have withdrawn from treatment will also complete a final CAPS-5 assessment immediately upon withdrawal. The IR will also administer the DSP-I and SDS.

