5.3.4 Early Termination from the Study

Participants who are removed from the study after they are enrolled and receive IP but do not complete the study may fall into one of these categories: Post-Dosing Early Termination or Dropout. If the participant has received IP in at least one Experimental Session and completed one CAPS-5 assessment beyond Baseline, they will be considered evaluable. All participants who receive IP in at least one Experimental Session will be included in all safety analyses.

Participants can withdraw from treatment or withdraw consent at any time for any reason without judgment. The site team can withdraw a participant if, in their clinical judgment, it is in the best interest of the participant or if the participant cannot comply with elements of the protocol that are critical for safety or for the scientific integrity of the study. If the site team makes the decision to terminate the participant from treatment or the study, they will explain the reason for withdrawal and document in the participant's source records and eCRF. If a participant develops any Exclusion Criteria that, in the opinion of the Medical Monitor or Site, affects the safety of the participant, including psychiatric diagnosis, pregnancy, or requiring use of prohibited medications, the participant will discontinue treatment in Experimental Sessions but remain in the study for the associated Integrative Sessions. Any time a participant terminates from the study early, the site team will attempt to obtain information about AE outcomes if appropriate, as determined by the site physician and Medical Monitor. The site team will provide the participant with an Exit Plan as described in Section 8.4.3.2 Exit Plan.

 Post-Dosing Early Termination: Participants who discontinue study treatment but continue to participate in study evaluations and outcome assessments. Data collection by IRs will continue on the same schedule as planned through Study Termination visit procedures.

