8.3.1 Experimental Sessions

There will be three open-label Experimental Sessions (Visits 5, 10, 15). Procedures for MDMA-assisted psychotherapy will remain the same across all sessions and all procedures regardless of

dose received. Experimental Sessions must be at least 8 hours long, measured from 30 minutes prior to IP administration.

Experimental Session 1 (Visit 5) will occur within 1 week of the Baseline CAPS-5 (Visit 3) assessment. If the Baseline CAPS-5 assessment is completed outside of the allowed window, the investigator should consult the CRA and Medical Monitor to determine if the assessment should be repeated. The first Experimental Session will include 80 mg of IP followed by a supplemental half-dose 1.5 to 2 hours after the initial dose unless contraindicated.

MP16 Protocol

- Experimental Session 2 (Visit 10) will occur within 3 to 5 weeks of Experimental Session 1 (Visit 5) and after Integrative Session 1.3. A dose of 80 or 120 mg MDMA will be administered. A supplemental half-dose will be administered 1.5 to 2 hours after the initial dose unless contraindicated.
- Experimental Session 3 (Visit 15) will occur within 3 to 5 weeks of the second Experimental Session (Visit 10) and after Integrative Session 2.3. A dose of 80 or 120 mg MDMA will be administered. A supplemental half-dose will be administered 1.5 to 2 hours after the initial dose unless contraindicated.

Table 7: Schedule of	f Procedures	s for Experimenta	l Sessions
----------------------	--------------	-------------------	-------------------

Approximate Time	Procedure or Action
9:30	Urine drug screen and pregnancy test, concomitant medication
	information collected, participant acclimated to environment, C-SSRS
9:55	Baseline BP, body temperature, pulse
10:00	IP Administration, Begin video recording
11:30	BP, body temperature pulse
	Supplemental Dose Administration, unless contraindicated
17:30	C-SSRS, BP, body temperature, pulse

Pre-IP administration

- On the day of the Experimental Session, the participant will arrive approximately 30 to 60 minutes prior to IP administration.
- The site team will ensure the participant has not used caffeine or nicotine 2 hours prior, and fasted for 10 hours prior to IP administration and complied with all other requirements per Section 4.3 Lifestyle Modifications.

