8.4.3 Study Termination

Study Termination (Visit 20) will take place 2 (-1/+7) days after the final CAPS-5 assessment (Visit 19). Participants who have withdrawn from treatment but have continued for follow-up will also complete this assessment immediately upon withdrawal.

The site team will:

- Inquire about any possible changes in health. Assess the participant's mental health and the status of any previously recorded AEs. Record AEs as described in Section 11.0 Safety.
- Inquire about concomitant medication use and adherence.
- Administer Since Last Visit C-SSRS.
- Measure weight (used to calculate BMI).
- Measure blood pressure.
- Provide and discuss a study exit plan.
- Ask them to enroll into the LTFU extension study with a visit at 12 months after the last experimental session. Review contact information and Informed Consent procedures for LTFU
- Actively support participant in completion of Study Termination self-reported measures:
 - o LEC-5
 - o PCL-5- ensure assessment is in relation to index trauma
 - o BDI-II
 - CPGS
 - o EQ-5D-5L
 - o IASC
 - o IPF
 - o SCS
 - o TAS-20
 - o AUDIT
 - o DUDIT
 - o SRNU
 - EAT-26
 - HPQSF

Completion of the measures do not need to be recorded.

After all Study Termination measures and assessments are completed, the participant is considered terminated from the study. The participant can resume normal everyday life. The study team will provide an Exit Plan, which may include a referral for additional medical or therapeutic care, as described in Section 8.4.3.2 Exit Plan. Eligible participants will be asked to participate in the LTFU extension study, described in Section 8.4.3.1 Extension Studies.

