## 8.2 Missing Data Handling

All possible procedures within Good Clinical Practice (GCP) will be used to minimize Postdosing Early Termination. Based on Phase 2 data it is expected that up to 5% of enrolled and

randomized participants will terminate early. Post-dosing Early Terminators will be compared to the Completers using baseline demographics and CAPS-5 Total Severity Score at baseline. Participants who are removed from the study after they are enrolled and receive IP but do not complete the study may fall into one of these categories: Post-Dosing Early Termination or Dropout. If the participant has received IP in at least one Experimental Session and completed one CAPS-5 assessment beyond Baseline, they will be considered evaluable. All participants who receive IP in at least one Experimental Session will be included in all safety analyses. Post-Dosing Early Termination are participants who discontinue study treatment but continue to participate in study evaluations and outcome assessments. Data collection by IRs will continue on the same schedule as planned through Study Termination visit procedures. Dropouts are defined as a participant who decides to withdraw consent. They will terminate without further follow-up. If the participant agrees, they will complete a final CAPS-5 assessment and Study Termination visit procedures. These participants are defined as dropouts who withdraw consent due to any reason after receiving at least one dose of IP and no longer participate in the study, i.e. no further contact with investigators or site staff. Data collected on study participants up to the time of withdrawal of consent will remain in the trial database in order to maintain scientific validity. Removal of data from the database would undermine the scientific and ethical integrity of the research. All observed CAPS-5 data up to the point of discontinuation of treatment will be included in the MMRM model of the *de jure* estimand from Post-dosing Early Terminators. Participants will not be replaced. All observed CAPS-5 data from Post-dosing Early Terminators and Dropouts collected prior to and after early termination will be included in the supportive effectiveness analysis of the *de facto* estimand.

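### The protocol gives two conflicting times for the last CAPS-5 of participants who stop treatment but stay in the study, and the SAP has no rule for an early score

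*Protocol*

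**What the plan says.** **Planned schedule.** Protocol 5.3.4 defines Post-Dosing Early Termination as "Participants who discontinue study treatment but continue to participate in study evaluations and outcome assessments", and adds for this group: "Data collection by IRs will continue on the same schedule as planned through Study Termination visit procedures". SAP 8.2 repeats the rule. Protocol 9.4 commits the sponsor to monitoring for complete data from all participants, including those who discontinue treatment.

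**Immediate.** Protocol 8.4.2, on the final rater assessment, says: "Participants who have withdrawn from treatment will also complete a final CAPS-5 assessment immediately upon withdrawal". Protocol 8.4.3, on the Study Termination visit, says: "Participants who have withdrawn from treatment but have continued for follow-up will also complete this assessment immediately upon withdrawal". The same section then states: "After all Study Termination measures and assessments are completed, the participant is considered terminated from the study".

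**Other rules on leaving treatment.** Section 12.3 has participants who take an antidepressant withdrawn from treatment and continuing in follow-up. Section 11.3.3 (pregnancy) mentions the next CAPS-5 assessment and also, as a minimum before withdrawal from the study, an immediate final CAPS-5.

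**Use of the data.** Under SAP 8.2 and 8.7.1 the primary de jure model uses CAPS-5 data up to discontinuation of treatment and omits data collected after it. For the de facto estimand, SAP 8.2 says that all CAPS-5 data from early terminators and dropouts "collected prior to and after early termination will be included in the supportive effectiveness analysis".

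**The concern.** The two instructions cover the same people and cannot both be followed as written. Someone who completes Study Termination on stopping treatment is out of the study and has no planned visit at which an 18-week CAPS-5 could be taken.

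The stake is the de facto analysis. It is the only planned analysis that uses CAPS-5 data collected after treatment stops, so it depends on treatment-stoppers having an outcome at the primary time point. If sites follow 8.4.2 and 8.4.3, those participants supply an off-schedule score instead. The SAP does not say whether that score counts as Visit 19, as the nearest scheduled visit or as unscheduled. Nor does it say on which side of discontinuation a score taken at the moment of withdrawal falls, and that decides whether it enters the de jure model.

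**Working it through.** The documents state no figure for this point, so there is none to reproduce. The check is a comparison of texts, then timing, then scale.

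**1. Same population?** Section 5.3.4 concerns people off treatment who are still assessed. Section 8.4.2 concerns people withdrawn from treatment. Section 8.4.3 concerns people withdrawn from treatment who have continued for follow-up. The populations overlap, and 8.4.3 describes the 5.3.4 group almost exactly.

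**2. When would an immediate score fall?** Weeks after Baseline (Visit 3), within the protocol windows:
- Session 1: 0 to 1, since "Experimental Session 1 (Visit 5) will occur within 1 week of the Baseline CAPS-5 (Visit 3) assessment".
- Session 2: 3 to 5 weeks after Session 1, so 0 + 3 = 3 to 1 + 5 = 6.
- Session 3: 3 to 5 weeks after Session 2, so 3 + 3 = 6 to 6 + 5 = 11.
- Visit 19: the "assessment must be completed 18 weeks (+/- 3 weeks) after the Baseline CAPS-5 assessment", so 18 − 3 = 15 to 18 + 3 = 21.

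| Treatment stopped | Immediate CAPS-5 (weeks) | Shortest gap to the Visit 19 window |
|---|---|---|
| After Session 1, before Session 2 | about 0 to 6 | 15 − 6 = 9 weeks |
| After Session 2, before Session 3 | about 3 to 11 | 15 − 11 = 4 weeks |

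In neither case can the immediate score serve as an in-window Visit 19.

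**3. How many participants?** Inputs: N up to 60 (Protocol 5.1) and early termination of up to 5% (SAP 8.2).
- Expected number: 60 × 0.05 = 3.
- Chance of at least one, if the rate is 5%: 1 − 0.95^60 = 0.954.

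The 5% covers early termination in general, so it stands in for the Post-Dosing Early Termination group and is better read as a ceiling.

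**4. How far could the mean move?** Assumption, with no figure in the documents: the early score differs from the 18-week score by d = 5 to 10 points and is counted as Visit 19. For a simple mean over N participants with k affected, the shift is k × d / N.
- d = 5: 3 × 5 / 60 = 0.25 points.
- d = 10: 3 × 10 / 60 = 0.50 points.

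The SAP does not specify the de facto estimator, so this shows scale only.

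**The case against.** The best defence is that 8.4.2 says these participants *also* complete an assessment at withdrawal, which could mean an extra rating on top of Visit 19. Section 5.3.4, section 9.4 and SAP 8.2 all point to continued collection, and 8.4.2 itself ties the primary assessment to 18 weeks. This stands in part: the documents do not plainly order Visit 19 to be skipped, and a reader who infers that it will never be collected goes too far. The defence does not remove the conflict. Section 8.4.2 calls the immediate rating final, and 8.4.3 ends participation at once even for those continuing follow-up. Reading withdrawal as leaving the study fails too, because both sentences speak of withdrawal from treatment.

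The objection that the consequence is small also stands. The primary analysis omits post-discontinuation scores, the affected analysis is supportive, and 0.5 points is one twentieth of the 10-point reduction that SAP 8.7.4 calls clinically meaningful.

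Three further inferences are tempting but unsupported:
- **Applying the 7.5% (8 of 107) from Protocol 2.2.4.** That is a dropout rate. Dropouts who withdraw consent generally lack Visit 19 under either text.
- **Treatment-stoppers are those who do worst.** Neither document says so.
- **The early score will be coded as Visit 19.** No text does this. What can be shown is that the SAP has no mapping rule.

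**Conclusion.** The concern holds as an internal inconsistency: wrong as written. Sections 8.4.2 and 8.4.3 contradict 5.3.4 and SAP 8.2 on when treatment-stoppers who remain in the study have their last CAPS-5. A site following the former might leave the de facto analysis with no 18-week value for them.

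The reach is limited to about 3 of 60 participants at most, on the SAP's 5% ceiling as a proxy. A shift of 0.25 to 0.5 points in a simple mean rests on the assumed 5 to 10 point difference and on the early score being counted as Visit 19. The larger loss is the valid 18-week outcome itself, for the group whose later data only this analysis uses.

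A reader might infer that the primary result is compromised. The documents do not support that. The primary analysis is touched only at the boundary, where the SAP leaves unclear whether a score taken at withdrawal belongs before or after discontinuation. The point should be corrected, but it does not threaten the trial's main estimate.

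**What to change.** **Protocol.** Reconcile the assessment timing in 8.4.2 and 8.4.3 with 5.3.4 and SAP 8.2:
- Participants who stop treatment but remain in the study still have the Visit 19 CAPS-5 at 18 (±3) weeks after Visit 3. The Baseline anchor is the usable one, since a participant without Session 3 has no date from which to count the 8 weeks.
- Any CAPS-5 at withdrawal from treatment is an additional early-termination assessment.
- The immediate final assessment is kept for people leaving the study.

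Sections 11.3.3 and 12.3 should be reconciled in the same edit, so that assessment timing after stopping treatment reads the same throughout. Only assessment timing is at issue; no change to the clinical rules in those sections is proposed.

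**SAP.** State that an early-termination score is not mapped to Visit 19, and whether it counts as before or after discontinuation for the de jure model.

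**Cost.** A protocol clarification, two sentences in the SAP, and up to one extra telemedicine rating for a few participants. There is also a burden on participants: under 8.4.1 and 12.1, concomitant-medication requirements run until Study Termination, so those who would otherwise have been terminated at once stay under them for longer. The sponsor should weigh that openly when reconciling the sections.

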8.4.3 Study Termination

Study Termination (Visit 20) will take place 2 (-1/+7) days after the final CAPS-5 assessment (Visit 19). Participants who have withdrawn from treatment but have continued for follow-up will also complete this assessment immediately upon withdrawal.

The site team will:

- Inquire about any possible changes in health. Assess the participant's mental health and the status of any previously recorded AEs. Record AEs as described in Section 11.0 Safety.
- Inquire about concomitant medication use and adherence.
- Administer Since Last Visit C-SSRS.
- Measure weight (used to calculate BMI).
- Measure blood pressure.
- Provide and discuss a study exit plan.
- Ask them to enroll into the LTFU extension study with a visit at 12 months after the last experimental session. Review contact information and Informed Consent procedures for LTFU
- Actively support participant in completion of Study Termination self-reported measures:
 - o LEC-5
 - o PCL-5- ensure assessment is in relation to index trauma
 - o BDI-II
 - CPGS
 - o EQ-5D-5L
 - o IASC
 - o IPF
 - o SCS
 - o TAS-20
 - o AUDIT
 - o DUDIT
 - o SRNU
 - EAT-26
 - HPQSF

Completion of the measures do not need to be recorded.

After all Study Termination measures and assessments are completed, the participant is considered terminated from the study. The participant can resume normal everyday life. The study team will provide an Exit Plan, which may include a referral for additional medical or therapeutic care, as described in Section 8.4.3.2 Exit Plan. Eligible participants will be asked to participate in the LTFU extension study, described in Section 8.4.3.1 Extension Studies.

8.4.3.1 Extension Studies

Upon completion of the study, defined as completing at least one Experimental Session and one CAPS assessment beyond Baseline, participants will be asked to join the LTFU extension study. The ICF for this study will be provided to eligible participants at the Study Termination visit. This study will measure outcomes 12 months after the last Experimental Session.

8.4.3.2 Exit Plan

At Study Termination, participants will be provided with an Exit Plan. This Exit Plan will summarize treatments completed, current medications, and contact information for more information about the study if needed. Participants may request a referral for further therapeutic or medical care if appropriate. Enrolled participants who terminate the study early will be provided an Exit Plan at their last contact. Screen Failures will be provided a referral if requested.

9.0 Investigational Product

9.1 Description of Active Compounds

The Active Pharmaceutical Ingredient (API) to be used in this protocol is MDMA. This ring-substituted phenethylamine has a complex pharmacology, but it acts most prominently as a monoamine releaser and re-uptake inhibitor. Its direct actions on serotonergic, adrenergic, and other receptors are considerably lower. Refer to the IB for a comprehensive review of the pharmacology, effects and proposed mechanisms of action of the IP. Lactose will serve as an inactive excipient.

9.1.1 Doses

This study will compare the effects of three open-label manualized Experimental Sessions of psychotherapy assisted by flexible doses of MDMA. Initial doses per Experimental Session include 80 mg or 120 mg MDMA compounded with lactose, followed 1.5 to 2 hours later by a supplemental half-dose (40 mg or 60 mg). Total amounts of MDMA to be administered per Experimental Session range from 80 mg to 180 mg. Refer to Table 5: Dose Regimen of MDMA.

9.1.2 Dose Modifications

In the first Experimental Session, the initial dose will be 80 mg MDMA. In the second and third Experimental Sessions, the initial dose may be increased to 120 mg MDMA unless contraindicated. The choice of whether to keep the dose the same or change it from the first Experimental Session will be made by the therapy team in consultation with the site physician based on observed response, tolerability to the previously administered dose, and discussion with the participant. In each Experimental Session, 1.5 to 2 hours after the initial dose is given, the participant will be administered a supplemental half-dose unless contraindicated.

9.1.3 Stability

Complete details on the chemistry, manufacturing and control of the MDMA hydrochloride (HCl) to be used are described in Drug Master file (DMF) # 6293. As described in that file, MDMA was prepared for human consumption by [name]., Department of Medicinal Chemistry and Pharmacology, Purdue University in 1985. The identity and purity of this MDMA was confirmed using High Performance Liquid Chromatography (HPLC) in 1997 as described in DMF # 6293 and was found to be 99.87% pure. On August 12, 2002, Chemic Laboratories reanalyzed the MDMA at the request of the sponsor in relation to the study of MDMA-assisted psychotherapy in people with PTSD, the analysis found it to be more than 99.7% pure. A more recent analysis performed by [name] at the request of researcher [name] in February 2006 continued to find a high degree of purity, with the analysis finding the MDMA in question to be 99.9% pure. The latest analyses conducted in May 2017 support that the MDMA is 100.0% pure by HPLC. All required Chemistry Manufacturing and Control (CMC) submissions will be made to the IND.

